5.7. Data collection and retrieval steps

3.7.1. Before surgery

Patients with coronary heart disease and heart valve disease who were indicated for cardiac surgery were determined to be eligible for the study based on the inclusion and exclusion criteria through history taking, physical examination, and the results of supporting examinations (electrocardiography, cardiac enzymes, and laboratory) obtained from the

patient's medical record at RSPJNHK. Furthermore, researchers conducted *informed consent* to patients who were eligible to become research subjects and asked for written consent from patients. Patients who agreed to the *informed consent* were randomized into treatment or control (placebo) groups. A research assistant carried out randomization using the "randomizer.org" site. The treatment group in this study received 5 g of tranexamic acid in 50 mL of 0.9% NaCl solution administered topically to the pericardial cavity after protamine administration and before sternotomy closure. In contrast, the control group (placebo) received 100 mL of 0.9% NaCl solution without tranexamic acid administered in the same way as the treatment group. The pharmacy department prepared the preparations in the study so that neither the researchers nor the patients were aware of the preparations used intraoperatively.

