3.1. Research design

This study used a randomized clinical trial, placebo-controlled and double-blinded.

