3.7.2. Perioperative

Patients who became research subjects underwent coronary artery bypass surgery according to standard operating procedures at RSPJNHK. After inducing anesthesia, undergoing sternotomy, and installing a heart-lung bypass machine (*on-pump*), the patient underwent the primary procedure. Then the research protocol was carried out with either treatment or control (placebo) after the heart-lung bypass machine stopped and before the sternum was closed by previously clamping the chest tube. After skin closure was completed, the chest tube clamps were reopened, and internal suction was performed, followed by connecting the chest tube with a *water-sealed drainage* system to accommodate post-surgical intrathoracic bleeding. The sternal closure to skin suturing process is done within 30-45 minutes.

In OPCAB group, after the graft anastomosis with OPCAB technique was completed, before sternal closure, the patient was given an intervention in

the form of topical tranexamic acid (5g/50mL) or placebo (50mL normal saline) dissolved in 100mL normal warm saline (37° C) which was inserted into the pericardial cavity including mediastinal tissue and allowed to stand for five minutes. It was then cleaned and sternal closure was performed.

The study subjects then underwent heart valve surgery according to the standard operating procedures of RSJPDHK, which began with induction of anesthesia, sternotomy, and CPB insertion. After the heart-lung bypass machine stopped, the chest tube was installed and clamped, the Subject then received one of the placebo or treatment fluids which were divided into two administrations, 50 mL of the first liquid was given to the intrapericardium and 50 mL of the second liquid was given to the sternum. The sternum was closed to the skin with an estimated completion of 30-45 minutes. Chest tube clamps were opened and connected to a water-sealed drainage (WSD) system to remove residual bleeding in the thorax after surgery.

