3.10. Operational Definition

Table 3.2 Operational definitions-

| Variables | Definition | Measurement | Variable Scale | Variable Value |
|--|--|---|----------------|--|
| Administration of topical tranexamic acid | Intrapericardial administration of 5 g tranexamic acid in 50 mL 0.9% NaCl after protamine administration and before sternotomy closure in cardiac surgery | - | Nominal | 
 • Treatment (tranexamic acid) • Control (NaCl 0.9%) |
| Amount of bleeding | | | | |
| Initial bleeding | Amount of blood accumulated in the patient's water-sealed drainage (WSD) system shortly after cardiac surgery | Observation of the volume of blood collected in the WSD system | Numerical | mL |
| 6-hour bleeding | Amount of blood accumulated in the water-sealed drainage (WSD) system of a patient 6-hour post cardiac surgery | Observation of the volume of blood collected in the WSD system | Numerical | mL |
| 24-hour bleeding | Amount of blood accumulated in the water-sealed drainage (WSD) system of a patient 24 hour-post cardiac surgery | Observation of the volume of blood collected in the WSD system | Numerical | mL |
| 48-hour bleeding | Amount of blood accumulated in the water-sealed drainage (WSD) system of a patient 48 hours- post cardiac surgery | Observation of the volume of blood collected in the WSD system | Numerical | mL |
| Blood Transfusion Requirements | | | | |
| Packed red cell (PRC) transfusion | Amount of PRC transfusions received in post cardiac surgery patients with Hb levels <10 g/dL to reach Hb levels >10 g/dL before discharge. | Observation of the volume of PRC received by the patient | Numerical | mL |
| Platelet transfusion ⁴⁹ | Amount of blood platelet transfusions received in post cardiac surgery patients with platelets <100,000 U/ μ L to reach levels of 100,000 U/ μ L or in platelet dysfunction. | Observation of the volume of Platelet transfusion received by the patient | Numerical | mL |
| Fresh Frozen plasma (FFP)Transfusion ⁴⁹ | Amount of blood FFP transfusions received by post cardiac surgery patients with international normalized ratio (INR) >1.5 to reach 1.5 | Observation of the volume of FFP received by the patient | Numerical | mL |

| Variables | Definition | Measurement | Variable Scale | Variable Value |
|---|---|--|----------------|---|

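### Section 3.7.1 puts tranexamic acid in 50 mL but placebo at 100 mL; followed literally for CABG, the surgeon could tell the arms apart

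*Combined protocol and SAP*

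**What the plan says.** Section 3.1 sets the design: "This study used a randomized clinical trial, placebo-controlled and double-blinded". Section 3.7.1 describes the intervention for all randomised patients. For the active arm it states: "The treatment group in this study received 5 g of tranexamic acid in 50 mL of 0.9% NaCl solution administered topically". It then contrasts this with placebo: "the control group (placebo) received 100 mL of 0.9% NaCl solution without tranexamic acid administered in the same way as the treatment group". Blinding is left to preparation by the pharmacy, "so that neither the researchers nor the patients were aware of the preparations used intraoperatively". Nothing is said there about matched volumes or containers.

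Other places bear on the volume:

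- Table 3.2 (section 3.10) defines the treatment as "Intrapericardial administration of 5 g tranexamic acid in 50 mL 0.9% NaCl after protamine administration and before sternotomy closure in cardiac surgery". It gives the control only as 0.9% saline, without a volume.
- Section 3.7.2, OPCAB: the intervention takes "the form of topical tranexamic acid (5g/50mL) or placebo (50mL normal saline) dissolved in 100mL normal warm saline".
- Section 3.7.2, valve surgery: whichever fluid is allocated, "50 mL of the first liquid was given to the intrapericardium and 50 mL of the second liquid was given to the sternum".
- Section 3.7.2, CABG: "Then the research protocol was carried out with either treatment or control (placebo) after the heart-lung bypass machine stopped". No volume is given.
- Table 3.3 (section 3.13) has the surgeon give the drug, described as 5 g in 50 mL, or placebo in 100 mL, with 50 mL instilled after protamine and 50 mL before sternal closure. The 100 mL may apply to both fluids or to placebo alone.

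**The concern.** A pharmacy can hide what a clear fluid contains. It cannot hide from the person instilling it whether there is 50 mL or 100 mL. If section 3.7.1 is followed as written, that person is the surgeon (Table 3.3), and the arm becomes recognisable while the chest is still open.

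Two routes to bias would then be open. The first is haemostasis before closure, which is in the surgeon's hands and directly affects the drain-volume endpoint. The second is platelet transfusion, which Table 3.2 allows for platelet dysfunction as well as for a low count.

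The same conflict leaves the CABG drug concentration undefined, so the intervention cannot be reproduced from the text even if the blind holds.

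**Working it through.** **Inputs.** Volumes come from sections 3.7.1 and 3.7.2 and Tables 3.2 and 3.3. Patient numbers come from section 5.6: 20 per arm plus 2 for dropout gives 22; 22 × 2 = 44 per surgery type; 44 × 3 = 132 in total. These numbers reproduce and do not depend on this point.

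**Volumes side by side.**

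| Source | Active | Placebo | Placebo ÷ active |
|---|---|---|---|
| 3.7.1, all patients, read literally | 50 mL | 100 mL | 100/50 = 2.0 |
| Table 3.2 | 50 mL | not stated | – |
| 3.7.2, OPCAB | 50 mL with 100 mL warm saline | 50 mL with 100 mL warm saline | 1.0 |
| 3.7.2, valve | 50 + 50 = 100 mL | 50 + 50 = 100 mL | 100/100 = 1.0 |
| 3.7.2, CABG | not stated | not stated | – |
| Table 3.3, equal reading | 50 + 50 = 100 mL | 50 + 50 = 100 mL | 100/100 = 1.0 |
| Table 3.3, unequal reading | 50 mL | 100 mL | 100/50 = 2.0 |

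The OPCAB ratio is 1.0 whether the final volume is taken as 100 mL or 150 mL.

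**Where the conflict lies.** The explicit contradiction is between 3.7.1 and the OPCAB and valve paragraphs of 3.7.2. Those paragraphs are specific to their procedures and give equal volumes, so following them protects the blind. For CABG, 3.7.2 is silent. That leaves 3.7.1 as the only narrative volume, and Table 3.3 as the only other text covering placebo volume. No text states one final CABG volume for both arms.

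**Patients whose allocation could be seen in theatre.**

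- Equal reading of Table 3.3: 0 of 132.
- 3.7.1 followed literally for CABG: up to 44 of 132, and 44/132 = 33.3%.

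**Drug concentration for CABG.**

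- 3.7.1 read literally: 5000 mg / 50 mL = 100 mg/mL.
- Equal reading of Table 3.3: 5000 mg / 100 mL = 50 mg/mL.

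**A secondary effect on the endpoint.** In the CABG paragraph the chest tube is clamped before instillation and reopened after skin closure, and no removal of the fluid before closure is described. If volumes were unequal, the extra placebo fluid is 100 − 50 = 50 mL. I assume that between 0 and 50 mL of it reaches the measured drainage. The upper end is 50/300 = 17% of the 300 mL difference used in section 5.6, in the direction that favours the drug. The suction described at clamp release, before the drainage system is connected, may remove some or all of it, so this is a range and not an estimate.

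**The case against.** The best counter-argument is that section 3.7.1 is a drafting slip and the fluids are matched. Table 3.3 sets out a single operating-room step, and 50 mL plus 50 mL cannot be drawn from a 50 mL active preparation, so the unequal reading works only if the schedule applies to placebo alone. Section 3.7.1 itself says placebo is given in the same manner as the drug. The OPCAB paragraph uses 5 g per 50 mL for the drug component before it goes into further saline, so 3.7.1 and Table 3.2 may simply have left out the final dilution. Two of the three surgery types are plainly matched, and nobody appears to have chosen an unmatched placebo.

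Much of this stands. The equal reading of Table 3.3 is the better one, and 44 of 132 is a conditional ceiling. It also requires that the pharmacy issue visibly different volumes and that the surgeon know which belongs to which arm.

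The bias routes are limited as well:

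- Bleeding is a measured drain volume.
- One researcher makes all observations, although the plan does not say whether that person is in theatre.
- Red cells, plasma and cryoprecipitate follow laboratory thresholds.
- Section 3.7.3 gives only a count threshold for platelets; the dysfunction criterion appears only in Table 3.2. Nothing says the operating surgeon orders them.

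The argument does not supply the missing statement. Section 3.7.1 mentions no dilution and draws an explicit contrast between the arms, Table 3.2 repeats 50 mL, and no text fixes the CABG volume. An objective measurement does not protect against a difference in haemostasis before closure. A slip in a dosing instruction still needs correcting, because pharmacy and theatre staff work from it.

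**Conclusion.** The concern holds. Section 3.7.1 states unequal volumes that contradict the equal volumes given for OPCAB and valve surgery, and nothing states a common final volume for CABG.

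For CABG the placebo-to-active volume ratio is 1.0 or 2.0, and the drug concentration is 50 or 100 mg/mL, depending on which text is followed. Allocation could be visible in theatre for 0 to 44 of 132 patients. The upper figure assumes that 3.7.1 is followed literally for CABG and that the surgeon recognises the volumes. The lower figure assumes the equal reading of Table 3.3.

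The documents do not show that unblinding took place, and no size of bias is claimed. This should be fixed. Confidence is moderate, because the equal reading may be what was intended and done.

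**What to change.** Correct section 3.7.1 and Table 3.2, reword Table 3.3 so that the volume clearly applies to both fluids, and add a volume to the CABG paragraph of section 3.7.2. Within each surgery type, both arms should receive the same final volume in identical containers, with the same split between administrations and the same dwell time.

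For CABG, following the equal reading of Table 3.3, the text could be:

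> Tranexamic acid 5 g made up with 0.9% NaCl to a final 100 mL, or 0.9% NaCl 100 mL; in both arms, 50 mL after protamine and 50 mL before sternal closure.

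The OPCAB paragraph should also state its final volume, since it can be read as 100 mL (50 mg/mL) or 150 mL (5000/150 = 33.3 mg/mL).

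If treatment is already complete, report the volume actually given by arm and by procedure. If CABG volumes differed, describe the operating team as potentially unblinded for that group.

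The cost is protocol wording and a pharmacy preparation sheet. No extra patients or procedures are needed.

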3.7.2. Perioperative

Patients who became research subjects underwent coronary artery bypass surgery according to standard operating procedures at RSPJNHK. After inducing anesthesia, undergoing sternotomy, and installing a heart-lung bypass machine (*on-pump*), the patient underwent the primary procedure. Then the research protocol was carried out with either treatment or control (placebo) after the heart-lung bypass machine stopped and before the sternum was closed by previously clamping the chest tube. After skin closure was completed, the chest tube clamps were reopened, and internal suction was performed, followed by connecting the chest tube with a *water-sealed drainage* system to accommodate post-surgical intrathoracic bleeding. The sternal closure to skin suturing process is done within 30-45 minutes.

In OPCAB group, after the graft anastomosis with OPCAB technique was completed, before sternal closure, the patient was given an intervention in

the form of topical tranexamic acid (5g/50mL) or placebo (50mL normal saline) dissolved in 100mL normal warm saline (37° C) which was inserted into the pericardial cavity including mediastinal tissue and allowed to stand for five minutes. It was then cleaned and sternal closure was performed.

The study subjects then underwent heart valve surgery according to the standard operating procedures of RSJPDHK, which began with induction of anesthesia, sternotomy, and CPB insertion. After the heart-lung bypass machine stopped, the chest tube was installed and clamped, the Subject then received one of the placebo or treatment fluids which were divided into two administrations, 50 mL of the first liquid was given to the intrapericardium and 50 mL of the second liquid was given to the sternum. The sternum was closed to the skin with an estimated completion of 30-45 minutes. Chest tube clamps were opened and connected to a water-sealed drainage (WSD) system to remove residual bleeding in the thorax after surgery.

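### The one intervention is described inconsistently: Table 3.2 omits the sternal portion, drug content per valve portion is unstated, and 3.7.1 gives unequal active and placebo volumes

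*Combined protocol and SAP*

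**What the plan says.** Four places describe what goes into the chest.

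- **Section 3.7.1 (Before surgery).** The active group "received 5 g of tranexamic acid in 50 mL of 0.9% NaCl solution administered topically to the pericardial cavity". For placebo, the wording is that "the control group (placebo) received 100 mL of 0.9% NaCl solution without tranexamic acid administered in the same way as the treatment group". Both fluids are prepared by the pharmacy so that researchers and patients stay blind.
- **Table 3.2 (section 3.10).** The independent variable is defined without limit to surgery type: "Intrapericardial administration of 5 g tranexamic acid in 50 mL 0.9% NaCl after protamine administration and before sternotomy closure in cardiac surgery".
- **Section 3.7.2 (Perioperative).** For on-pump CABG it gives no volume or dose. The fluid goes in before sternal closure with the chest tube clamped. "After skin closure was completed, the chest tube clamps were reopened", then internal suction is applied and the drainage system is connected. For OPCAB the fluids are "5g/50mL) or placebo (50mL normal saline) dissolved in 100mL normal warm saline". On site and dwell, the same paragraph has the fluid "inserted into the pericardial cavity including mediastinal tissue and allowed to stand for five minutes", after which it is removed. For valve surgery the assigned fluid is divided: "50 mL of the first liquid was given to the intrapericardium and 50 mL of the second liquid was given to the sternum".
- **Table 3.3 (section 3.13).** For all patients, 5 g in 50 mL or placebo in 100 mL, given as 50 mL after protamine and 50 mL before sternal closure. No site and no grams per portion are given.

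**The concern.** Table 3.2 is where a reader looks for the treatment that was tested, and it does not match what 3.7.2 has the surgeon do. Valve patients receive fluid at the sternum, a site the definition leaves out, and neither portion's drug content is given. Table 3.3 splits the fluid for everyone, while the OPCAB text describes one fluid with a short dwell.

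Section 6.3.3 says no study has yet established whether concentration, total dose or contact time drives the topical effect. A plan that grants this should fix all three. Otherwise a valve result cannot be tied to the regimen in Table 3.2, or reproduced.

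The placebo wording in 3.7.1 raises a separate issue. Drain volume is the bleeding outcome, and initial bleeding is read on arrival in the ICU. If the placebo group received more fluid, the surgeon could recognise the group by volume. Any excess left in the chest would count as placebo bleeding and so favour tranexamic acid.

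**Working it through.** **1. The texts side by side**

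| Source | Applies to | Active | Placebo | Site | Division and removal |
|---|---|---|---|---|---|
| 3.7.1 | all | 5 g in 50 mL | 100 mL | pericardium | none stated |
| Table 3.2 | all | 5 g in 50 mL | volume not stated | pericardium | none stated |
| 3.7.2, on-pump CABG | CABG | not stated | not stated | not stated | tube clamped until skin closed, then suction |
| 3.7.2, OPCAB | OPCAB | 5 g/50 mL in 100 mL | 50 mL in 100 mL | pericardium and mediastinal tissue | single fluid, 5 min, cleaned out |
| 3.7.2, valve | valve | 50 + 50 mL, grams not stated | 50 + 50 mL | pericardium, then sternum | two portions |
| Table 3.3 | all | 5 g in 50 mL, given as 50 + 50 mL | 100 mL, given as 50 + 50 mL | not stated | two portions |

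In Table 3.3 the 100 mL may attach to the placebo alone or to both fluids.

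**2. Drug content of a valve portion (assumed readings, since none is stated)**

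- 5 g brought to 100 mL and halved: 5,000 mg / 100 mL = 50 mg/mL; 50 mL × 50 mg/mL = 2.5 g per site; total 5 g.
- 5 g in the pericardial 50 mL and plain saline to the sternum: 5 g + 0 g; total 5 g.

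With the total held at the stated 5 g, the pericardium receives 2.5 g or 5 g.

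**3. OPCAB concentration**

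- Final volume 100 mL: 5,000 / 100 = 50 mg/mL.
- 50 mL added to 100 mL: 5,000 / 150 = 33.3 mg/mL.

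**4. Placebo volume, on a literal 3.7.1**

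The yardstick is the planned 300 mL difference in section 5.6. That calculation reproduces: 2 × [(1.96 + 0.842) × 339.021 / 300]² = 20.05, against the stated 20 per group. It is used here only for scale.

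- Excess instilled: 100 − 50 = 50 mL.
- Excess reaching the drain: 0 to 50 mL.
- Ceiling: 50 / 300 = 16.7% of the planned difference. This assumes that none of the extra fluid is suctioned or absorbed.

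OPCAB and valve patients have equal volumes in both groups under 3.7.2. On-pump CABG has no volume there and so falls back on 3.7.1 or Table 3.3.

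**The case against.** One reading fits most of the text: 5 g/50 mL is the drug as prepared, and it is then brought to 100 mL. The OPCAB paragraph uses the phrase in this way. A 100 mL placebo given in the same way implies a 100 mL active volume, and Table 3.3 splits the fluid 50 + 50 mL. On that reading the volume gap between Table 3.2 and the valve text closes, and so does the placebo mismatch. Table 3.2 is also a one-line definition that may be incomplete rather than contradictory, and a pharmacy instruction outside these documents may already settle practice.

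Most of this stands, and it rules out several stronger inferences:

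- **That volumes conflict however the text is read.** They do not if 5 g in 50 mL is the pre-dilution preparation.
- **That valve patients might receive 10 g.** This needs both portions to carry 5 g. No section states it, and the valve text speaks of dividing the assigned fluid.
- **That contact lasts at least 30 to 45 minutes in on-pump CABG and valve surgery.** For CABG the text says "The sternal closure to skin suturing process is done within 30-45 minutes", which is not a minimum, and the valve figure is an estimate of completion. Neither is a stated contact time. OPCAB also has its own technique, hypotheses and results table, so a different dwell there is not in itself an error.
- **That the bleeding outcome is biased.** This requires following one clause of 3.7.1 against the rest of its own sentence, and suction before drainage may remove the excess.

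The favourable reading leaves four things untouched. It is never stated, the sternal site is still missing from the definition, grams per valve portion are still not given, and Table 3.3's split for all patients still conflicts with the single OPCAB fluid. Section 3.7.1 also still needs its volumes corrected. If the pharmacy instruction is sound, the protocol should be brought into line with it.

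**Conclusion.** The intervention is inconsistently described, and the description should be corrected. Four defects hold even on the most favourable reading: Table 3.2 omits the sternal site, the drug content of each valve portion is unstated, Table 3.3's two-portion rule for all patients conflicts with the OPCAB procedure, and 3.7.1 as written gives unequal volumes.

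The likely valve regimen is 2.5 g to each site, on the assumption that 5 g is brought to 100 mL and halved. The documents show no conflict in total dose. The volume mismatch matters only if 3.7.1 was followed literally, and in practice only for on-pump CABG. There it would compromise the surgeon's blinding and could add 0 to 50 mL to placebo drainage, at most 16.7% of the planned difference and possibly near zero.

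A reader might infer that the trial's comparisons are invalid. The documents do not support that. Hypotheses and results tables are separate by surgery type, so comparisons within a type remain valid where volumes are matched. No sample size or power figure changes. The loss is in attribution and reproducibility.

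**What to change.** 1. Correct 3.7.1 so that active and placebo have the same final instilled volume and the same split: 100 mL each, if the clinical team and pharmacy confirm.
2. Replace the treatment row in Table 3.2 with one row each for CABG, OPCAB and valve surgery. Each row states total grams (5 g), final volume, grams and site of each portion, and whether and when the fluid is removed.
3. Align 3.7.2 and Table 3.3 to these rows, and check them against the pharmacy instruction.
4. The schedule places the study in October to December 2022. If treatment is complete, establish from pharmacy records what was given, including volumes, and report it by surgery type and group.

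The cost is very low: edits to four places and one check with the pharmacy or, after completion, a review of pharmacy records. Which regimen is right is for the clinical team to say.
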